2.6 Analysis of key secondary objectives

Not applicable.

2.7 Analysis of secondary objectives

2.7.1 Secondary endpoints

The secondary efficacy endpoints are ORR, DCR, TTR, DOR as per RECIST 1.1 and OS. Estimation of all secondary endpoints will be provided by treatment arms based on the FAS. All relative listings, tables and figures will be presented by treatment arm, unless otherwise specified.

Objective response rate (ORR)

ORR is defined as the proportion of subjects with a BOR of CR or PR as per local review and according to RECIST 1.1.

BOR is defined as the best response recorded from the start of the treatment until disease progression/recurrence as per local review and according to RECIST 1.1.

Disease control rate (DCR)

DCR is defined as the proportion of subjects with a BOR of CR, PR or SD as per local review and according to RECIST 1.1.

Time to response (TTR)

TTR applies to all subjects. For responders, TTR is defined as the time from the date of randomization to the first documented response of either CR or PR, which must be subsequently confirmed (although initial date of response is used, not date of confirmation). For non-responders, TTR will be censored at the last adequate tumor assessment date if no PFS event occurs, otherwise, TTR will be calculated at the censored time from the first visit of the first subject to the last visit of the last subject.

Duration of response (DOR)

DOR is defined as the time between the date of first documented response (CR or PR) and the date of first documented progression or death due to underlying cancer.

Overall survival (OS)

OS is defined as the time from randomization to date of death due to any cause.

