16.1.3.2.7 Time to response

Time to overall response (CR or PR) is the time between date of randomization/start of treatment until first documented response (CR or PR). The response may need to be confirmed depending on the type of study and its importance. Where the response needs to be confirmed then time to response is the time to the first CR or PR observed.

Although an analysis on the full population is preferred a descriptive analysis may be performed on the “responders” subset only, in which case the results should be interpreted with caution and in the context of the overall response rates, since the same kind of selection bias may be introduced as described for duration of response in [Section 16.1.3.2.5](#). It is recommended that an analysis of all patients (both responders and non-responders) be performed whether or not a “responders only” descriptive analysis is presented. Where an inferential statistical comparison is required, then all patients should definitely be included in the analysis to ensure the statistical test is valid. For analysis including all patients, patients who did not achieve a response (which may have to be a confirmed response) will be censored using one of the following options:

- at maximum follow-up (i.e. FPFV to LPLV used for the analysis) for patients who had a PFS event (i.e. progressed or died due to any cause). In this case the PFS event is the worst possible outcome as it means the patient cannot subsequently respond. Since the statistical analysis usually makes use of the ranking of times to response it is sufficient to assign the worst possible censoring time which could be observed in the study which is equal to the maximum follow-up time (i.e. time from FPFV to LPLV)
- at last adequate tumor assessment date otherwise. In this case patients have not yet progressed so they theoretically still have a chance of responding

Time to overall complete response (CR) is the time between dates of randomization/start of treatment until first documented CR. Similar analysis considerations including (if appropriate) censoring rules apply for this endpoint described for the time to overall response endpoint.

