2.5.3 Handling of missing values/censoring/discontinuations

PFS will be censored at the date of the last adequate tumor assessment prior to the earliest cut-off date for the analysis, the start of a subsequent anti-neoplastic therapy (if any), the date of sponsor's decision to discontinue capmatinib (applicable only to subjects on the combination arm), or if the event occurred after two or more missing tumor assessments. Clinical progression without objective radiological evidence will not be considered as documented disease progression. Subjects should be followed after discontinuation of treatment to document clinical progression. The date of the last adequate tumor assessment is the date of the last tumor assessment with overall lesion response of CR, PR or SD before an event or a censoring reason has occurred. If no post-baseline assessments are available (before an event or a censoring reason occurred), the date of treatment randomization will be used.

The number of subjects censored and reasons for censoring will be summarized by treatment arm using descriptive statistics.

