2.7.3 Handling of missing values/censoring/discontinuations

Regarding ORR:

- Subjects in the FAS with unknown BOR will be noted as such in the appropriate tables/listings and counted as non-responders in the ORR calculation.
- If there is no baseline tumor assessment, all post-baseline overall lesion responses are expected to be 'Unknown'. If no valid post-baseline tumor assessments are available, the BOR must be "Unknown" unless progression or death is reported.
- If any new anti-neoplastic therapy is taken while on study, any subsequent assessments would be excluded from the BOR derivation.

- Confirmed PR or CR reported prior to any additional anticancer therapy will be considered as responses in the calculation of the ORR irrespective of the number of missed assessments before response.

Regarding DOR:

- If progression or death due to any reasons has not occurred by the date of the cut-off, then the subject will be censored following the same rules defined for PFS in [Section 2.5.3](#).
- If a subject with a CR or PR has no progression or death, the subject is censored at the date of last adequate tumor assessment.

Regarding OS:

- The last date the subject was known to be alive is the last date the subject was contacted or seen by the treating team. If no post-baseline dates are available (before death or a censoring reason occurred), the date of randomization will be used.
- If a subject is not known to have died by the date of the cut-off, OS will be censored at the last date the subject was known to be alive.

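### In the time-to-response Kaplan-Meier analysis, non-responders who start new anti-cancer therapy before progression are censored as if they could still respond, so the reported response probability can be too high

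*SAP*

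**What the plan says.** SAP 2.7.1 (and Protocol 12.5.1, in nearly the same words) applies TTR to all subjects and splits the non-responders in two:

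- With no PFS event: "TTR will be censored at the last adequate tumor assessment date if no PFS event occurs".
- With a PFS event: "TTR will be calculated at the censored time from the first visit of the first subject to the last visit of the last subject". This keeps the subject in the risk set to the end.

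Protocol 16.1.3.2.7 gives the reasons. After a PFS event the patient can no longer respond. For the others, "In this case patients have not yet progressed so they theoretically still have a chance of responding". The same section explains PFS event as progression or death from whatever cause.

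SAP 2.5.3 censors PFS when another anti-cancer therapy begins, at the sponsor's decision to stop capmatinib (combination arm only), "or if the event occurred after two or more missing tumor assessments". It adds: "If no post-baseline assessments are available (before an event or a censoring reason occurred), the date of treatment randomization will be used".

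SAP 2.7.3 states for response: "If any new anti-neoplastic therapy is taken while on study, any subsequent assessments would be excluded from the BOR derivation". It counts an unknown best response as a non-response in ORR, and it has no paragraph on TTR.

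SAP 2.7.2 reports TTR by arm as Kaplan-Meier medians, quartiles, curves and estimates at 3, 6, 12 and 18 months.

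**The concern.** Placing non-responders with a PFS event at maximum follow-up is sound: it makes one minus Kaplan-Meier (1-KM) behave like a cumulative incidence of response. Censoring the rest at their last scan is sound only if they can still respond. A subject who moves to new therapy without documented progression cannot, because SAP 2.7.3 excludes every later assessment.

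The rule appears to have been carried over from the sponsor's RECIST guideline. There the default is to ignore new therapy (Protocol Table 16-5, situation F, option 1), so that a later progression or death remains a PFS event. PFS in this study now censors at new therapy (Protocol 12.4.1.3), but the TTR rule was not adapted to match.

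Readers will take the Kaplan-Meier figures as the probability of response by a given month. ORR in the same report keeps these subjects in the denominator, so the two can disagree for a reason the report does not explain.

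**Working it through.** The documents give no TTR or ORR figure, so there is nothing to reproduce. The check compares 1-KM under the SAP rule with ORR = responders/N, then repeats it with the affected subjects at maximum follow-up.

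**Inputs from the documents.** Arm sizes 51 and 25 (Protocol summary, Population); scans every 9 weeks, ±7 days, through week 45 (Protocol 8.3.1).

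**Assumptions.** ORR 30-50%; 5-30% of non-responders affected; most first responses at weeks 9 and 18; affected subjects censored at day 1 or at weeks 9, 18 or 27. A subject censored on the day of a response counts as at risk that day.

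**Direction.** Kaplan-Meier passes the weight of each censored subject to those who remain. Once the last response has occurred, each responder carries weight of at least 1/N, so 1-KM ≥ responders/N. The two are equal when nobody is censored before a later response.

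**Example 1.** N = 25; 10 responders (6, 3 and 1 at weeks 9, 18 and 27); 3 of 15 non-responders affected, censored at day 1, week 9 and week 9.

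- Week 9: 24 at risk, factor 18/24.
- Week 18: 24 - 6 - 2 = 16 at risk, factor 13/16.
- Week 27: 13 at risk, factor 12/13.
- 1-KM = 1 - (18/24)(13/16)(12/13) = 0.4375. ORR = 10/25 = 0.400. With the three at maximum follow-up, 1-KM = 0.400.

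**Example 2.** N = 51; 20 responders (12, 6, 2); 6 of 31 non-responders affected (two at day 1, three at week 9, one at week 18).

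- 1-KM = 1 - (37/49)(28/34)(25/27) = 0.424. ORR = 20/51 = 0.392.

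**Example 3.** N = 51; 24 responders (15, 7, 2); the same six censoring times.

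- 1-KM = 1 - (34/49)(24/31)(21/23) = 0.510. ORR = 24/51 = 0.471.
- Survival falls below 0.5 at day 189, so a median of 189/30.4375 = 6.2 months is reported. With the six at maximum follow-up, the median is not reached.

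**Example with no excess.** N = 25; all 10 responses at week 9; affected subjects censored at week 9 or later: 1-KM = ORR = 0.400.

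**Simulation.** 1,500 replicates per setting; N = 25 and 51; ORR 30%, 40% and 50%; two response-timing patterns; affected subjects censored at day 1, week 9, 18 or 27 with probabilities 0.25, 0.40, 0.25 and 0.10; read at 18 months.

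| Non-responders affected | Mean excess of 1-KM over ORR (points) | Replicates with any excess, N = 25 |
|---|---|---|
| 5% | 0.6-0.9 | 41-56% |
| 10% | 1.2-1.8 | 66-81% |
| 20% | 2.5-3.8 | 90-96% |
| 30% | 4.0-6.1 | 97-99% |

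**Other censoring.** N = 51, the 20 responders of Example 2, nobody affected by new therapy, but 10 subjects censored at the sponsor's decision (one at day 1, four at week 9, three at week 18, two at week 27): 1-KM = 1 - (38/50)(28/34)(23/25) = 0.424 against ORR 0.392. An excess over ORR is therefore not in itself proof of the new-therapy problem.

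**The case against.** **Missed scans.** A reader might infer that subjects who progress or die after at least two missed scans are also wrongly censored, since SAP 2.5.3 discards their event for PFS. The documents do not settle this. Protocol 16.1.3.2.7 describes the TTR trigger as any progression or death, which read literally sends these subjects to maximum follow-up. The same reading covers someone who starts new therapy and later has a recorded progression or death. This part is an ambiguity to resolve before programming.

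**Size.** The affected share is assumed. The 26 of 76 subjects off treatment by 15-Mar-2021 (76 - 50, Amendment 3 study update) cannot stand in for it: that count can include progressions and deaths, which the rule handles correctly, and before Amendment 3 scans continued after discontinuation (Protocol 8.3.1 and 9.2.2.2). After Amendment 3 neither efficacy data nor post-discontinuation therapies are collected (Protocol 8.3 and 9.2.2.1), which limits how many subjects can be affected.

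**Bias between arms.** A reader might also infer more inflation in the combination arm. The Amendment 3 rationale reports more adverse events leading to interruption or discontinuation there. It does not report more new therapies or missed scans, and Protocol 6.7.2 lets one drug continue when the other stops. A difference between arms is conjecture.

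**Importance.** TTR is descriptive with no hypothesis (SAP 2.7.2), and ORR with an exact interval is reported beside it. That lowers the stakes but does not correct the TTR estimate.

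**Conclusion.** The point holds for non-responders who start new anti-neoplastic therapy before documented progression. Under the plan's own rules they cannot respond, yet they are censored on the ground that they can, and nothing else in the documents repairs this. The bias runs in one direction. Under the assumed ranges the mean excess over ORR is about 1 to 6 percentage points, and in some configurations a median is reported that would otherwise not be reached. It is wrong to say that TTR must exceed ORR: the excess is conditional, and at N = 25 with 5% affected it appeared in only about half of the replicates. The missed-scan group needs a clarifying statement. No test or sample size depends on any of this, but the correction is cheap and worth making before database lock.

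**What to change.** Replace the non-responder sentence in SAP 2.7.1, and align Protocol 12.5.1, along these lines:

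*Non-responders who start a new anti-neoplastic therapy, or who progress or die from any cause (including after two or more missed assessments), are censored at maximum follow-up (FPFV to LPLV). All other non-responders are censored at their last adequate assessment. In the combination arm, the main analysis uses only events and therapies up to the date of the sponsor's decision to stop capmatinib; subjects still at risk on that date are censored at their last adequate assessment before it. A supportive analysis uses all available data.*

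Reporting the cumulative incidence of response, with these outcomes as competing events, would serve the same purpose.

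The limit at the sponsor's decision date matters. Without it, combination-arm progressions after that date would enter TTR, although the main PFS and best-response analyses leave them out (SAP 2.5.3 and 2.7.2). Because the censoring at that date is genuine, 1-KM need not equal ORR after the change, and a footnote to the table should say so.

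The cost is a few sentences and a revised censoring flag, using data already collected. Reported TTR rates may become slightly less favourable.

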2.7.2 Statistical hypothesis, model, and method of analysis

No statistical hypothesis was made on secondary endpoints.

Regarding ORR and DCR:

ORR and DCR will be presented by treatment arm, along with their accompanying 95% Clopper-Pearson CI based on the exact binomial distribution (Clopper and Pearson 1934). Individual lesion measurements, overall response assessments per RECIST 1.1 as well as BOR will be listed by subject and assessment date.

Any subsequent tumor assessment after the date of sponsor's decision to discontinue capmatinib (applicable only to subjects on the combination arm), will be excluded from the BOR derivation. In addition, to explore the potential lasting effect of capmatinib, a supportive analysis of BOR will be performed with including tumor assessments after sponsor's decision to discontinue capmatinib.

Regarding DOR, TTR, and OS:

TTR, DOR and OS will be summarized by treatment arms using the KM estimators for the medians along with their accompanying 95% CIs, and 25th and 75th percentiles (Brookmeyer and Crowley 1982, Klein and Moeschberger 1997). KM estimates for TTR and DOR at timepoints (3, 6, 12, and 18 months), and KM estimates for OS at timepoints (6, 12, 18 and 24 months), along with 95% CI (Greenwood's formula, Kalbfleisch and Prentice 2002) will also be provided. The number (%) of events and subjects censored will also be summarized. KM curves will be provided as well.

DOR only applies to subjects for whom BOR is CR or PR. The remaining subjects will not be taken into account in the estimation of this endpoint. If there are at least 10 subjects with a confirmed BOR of CR or PR, the KM analysis will be conducted by treatment arm. In addition, descriptive summary statistics of DOR on responders (e.g., subjects achieving at least once CR or PR) only will also be presented. DOR will be categorized into time intervals (e.g., ≤ 3 months, $>3 - \leq 6$ months, $>6 - \leq 12$ months, >12 months) and frequency counts and percentages will be presented for the number (%) of subjects in each interval. In addition, for the following cumulative categories (e.g., ≥ 3 months, ≥ 6 months, ≥ 12 months), frequency counts and percentages will be presented for the number (%) of subjects in each category.

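### The duration-of-response bins and plain descriptive statistics do not separate censored from completed responses, and combination-only censoring makes responses look shorter in that arm

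*SAP*

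**What the plan says.** **Main DOR analysis.** SAP 2.7.2 summarises DOR by KM: medians with 95% CIs, quartiles, estimates at 3, 6, 12 and 18 months, curves, and counts of events and censored subjects. One sentence makes this conditional: "If there are at least 10 subjects with a confirmed BOR of CR or PR, the KM analysis will be conducted by treatment arm".

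**Added outputs.** The same section then adds "descriptive summary statistics of DOR on responders (e.g., subjects achieving at least once CR or PR) only will also be presented". It also states that "DOR will be categorized into time intervals" (up to 3, over 3 to 6, over 6 to 12, over 12 months), where "frequency counts and percentages will be presented for the number (%) of subjects in each interval". A second, cumulative set follows (at least 3, 6 and 12 months). No event/ongoing split, flag or restriction to completed responses is given. Protocol 12.5.1 plans only KM for DOR.

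**Censoring.** Under SAP 2.7.3, if there is no progression or death by the cut-off, "then the subject will be censored following the same rules defined for PFS in" SAP 2.5.3. That section censors at the last adequate tumor assessment before several dates. One of them, the sponsor's decision to discontinue capmatinib, is "applicable only to subjects on the combination arm".

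**Control data.** Protocol 8.3 stops eCRF capture of efficacy data once Amendment 03 (dated 21-Apr-2021) is approved.

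**The concern.** A KM estimate treats a response still ongoing at 2 months as lasting at least 2 months. A frequency bin or a plain mean treats it as lasting 2 months, the same as a relapse at 2 months. If most durations are censored, the bins mainly describe length of follow-up.

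With equal follow-up this understates both arms alike. Here follow-up for DOR is not equal: the combination arm stops at the sponsor's decision, and control runs at least 90 days longer (21-Jan to 21-Apr-2021). Percentages by arm would then differ even if responses were equally durable. Comparing anti-tumor activity between arms is a stated secondary objective, so they will be read as a comparison.

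**Working it through.** The documents give no DOR assumption or expected number of responders, so there is no stated figure to reproduce.

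**One scan history in each arm.** Take a subject randomized on 1-Sep-2020 (an illustrative date), scanned every 63 days (Protocol Table 8-3), responding at the first scan on 3-Nov-2020 and still in response. Duration = end − start + 1 day (Protocol 16.1.4.5.1); a month is 30.4375 days (SAP 2.1.1.3).

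- Combination, last scan before 21-Jan-2021 is 5-Jan-2021: 64 / 30.4375 = 2.1 months, so the bin is up to 3 months.
- Control to 21-Apr-2021, last scan 9-Mar-2021: 127 / 30.4375 = 4.2 months, bin over 3 to 6.
- Control to 1-Jul-2021, last scan 11-May-2021: 190 / 30.4375 = 6.2 months, bin over 6 to 12.

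The same ongoing response falls in three different bins.

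**Simulation with equal true DOR.**

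From the documents: 9-week scans; halt on 21-Jan-2021 with 51 combination and 25 control subjects; earliest control data stop 21-Apr-2021; no subject treated by 22-Jan-2020.

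Assumed: sponsor's decision date equal to the halt date; uniform accrual 1-Feb-2020 to 21-Jan-2021; first response at scan 1 (70%) or scan 2 (30%); exponential DOR with a 12-month median in both arms; progression seen at the next scan; response still present at a confirming scan before the arm's cut; 9-week scans throughout.

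| | Combination, to 21-Jan-2021 | Control, to 21-Apr-2021 | Control, to 1-Jul-2021 |
|---|---|---|---|
| Censored | 87% | 81% | 74% |
| Naive, up to 3 months | 30% | 21% | 11% |
| Naive, at least 6 months | 36% | 52% | 63% |

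**Correct value in this model.** A scan-detected duration of at least 6 months means no progression by the second scan after response (126 days), given none by the first (63 days). With a 12-month median of 12 × 30.4375 = 365.25 days, this is 2^(−63/365.25) = 0.887. KM recovers it in both arms (0.887 and 0.887). The naive figures fall short in both, and further short in the combination arm.

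**Source of the arm difference.** With both arms cut at 21-Apr-2021, the naive share at 6 months or more is 51.5% and 51.7%. The gap disappears; the understatement stays.

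**Sensitivity** (control to 21-Apr-2021, at least 6 months, combination against control):

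- True median 6 months: 31% against 45%.
- True median 24 months: 37% against 55%.
- Protocol accrual ramp, true median 12 months: 0% against 8% (up to 3 months: 89% against 54%).

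At trial size (51 and 25 subjects, response rates 30–50%), the naive mean was lower for combination in 72–88% of runs with control to 21-Apr-2021, where about half would be expected without bias.

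**The 10-responder condition.** The text does not say whether it applies per arm or overall. By the binomial:

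- Per arm, P(at least 10 of 25 control subjects respond) = 0.19, 0.58 and 0.89 at response rates of 30%, 40% and 50%, before unconfirmed responses are lost.
- Overall, P(at least 10 of 76) = 0.955 at 20% and above 0.999 at 30%.

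**The case against.** **KM is already the main DOR analysis.** The landmark estimates, curves and censoring counts are planned, and the bins come on top. This stands and limits the harm. It does not correct the bins, and the censoring counts are not tied to them.

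**The SAP does not say that censoring is ignored.** A reader might infer that it does; in fact it is silent. SAP Section 1 places output layouts in the TFL shells, which are not among the documents, and a split may exist there. What can be said is that the SAP text, followed as written, counts every responder and gives no rule for censored ones.

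**The 10-responder rule may well mean 10 overall.** A reader might conclude that the naive table will be the only control-arm result. That needs the per-arm reading; on the overall reading KM would very probably be run in both arms. The rule is ambiguous, no more.

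**A common cut-off would not bias the comparison.** This is correct: the gap comes from the combination-only date, which Amendment 03 introduced deliberately. Nor are all combination responses cut; those that progressed earlier are events. Also, SAP 2.7.3 can be read as keeping a combination progression after the sponsor's date as an event. In the same simulation that reading narrows the gap without reversing it.

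**Low stakes.** DOR carries no hypothesis, the study was halted for tolerability, and Protocol Appendix 1 already urges caution with responder-only summaries. This limits the severity.

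**Conclusion.** The point holds in a limited form. The added DOR bins, cumulative bins and plain descriptive statistics do not separate censored from completed durations. Under the inherited PFS censoring they understate DOR in both arms, and more in the combination arm.

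Under the stated assumptions the artificial gap at 6 months or more is about 16 percentage points (36% against 52%) with the earliest control data stop, and about 27 points (36% against 63%) with a stop on 1-Jul-2021. These sizes depend on assumed accrual, response timing, true DOR and control data stop, and on taking 21-Jan-2021 as the sponsor's decision date. The direction did not change in any scenario run; it requires only that control data run later than the combination cut.

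The documents do not support concluding that the DOR analysis as a whole is invalid. The KM analysis respects the censoring and showed no artefact here. Severity is minor to moderate.

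**What to change.** 1. In SAP 2.7.2, split every DOR bin into progressed/died and ongoing/censored, or replace the bins with the KM proportions already planned.
2. Drop the plain descriptive statistics, or replace them with a listing of individual durations with a censoring flag.
3. Report KM DOR in each arm whatever the number of responders. If a threshold is kept, state whether it is per arm or overall.
4. In SAP 2.7.3, state whether a combination-arm progression after the sponsor's decision counts as a DOR event. Consider a supportive DOR analysis without that censoring, as is planned for PFS and BOR.

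The cost is SAP wording and one table shell, with no new data. KM intervals in the 25-subject arm will be wide, which reflects the information available. Dropping the bins takes nothing away from Protocol 12.5.1, which plans only KM for DOR.
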